
Updated the following Other Endpoints to clarify oral glucose tolerance test (OGTT) values (in mmol/L) and glucose ranges:
 
 Change from baseline in percent of time spent in target blood glucose range of ≥ 70 to < 140 mg/dL (≥ 3.89 to < 7.77 mmol/L) as measured by 7-day continuous glucose monitoring (CGM) in subjects with cystic fibrosis-related diabetes (CFRD) at Week 48 Change from baseline in selected CGM parameters (including but not limited to percent of time spent between ≥ 140 and < 200 mg/dL [≥ 7.77 and < 11.10 mmol/L], percent of time spent ≥ 200 mg/dL [≥ 11.10 mmol/L], and maximum amplitude of glucose excursions [MAGE]) in subjects with CFRD at Week 48 	Synopsis, and Sections 7.3 and 12.3.3.5
Updated the definition of impaired glucose tolerance (IGT) to 2-hour post-OGTT blood glucose level ≥ 140 to < 200 mg/dL (≥ 7.77 to < 11.10 mmol/L) to eliminate a gap in glucose values in previous protocol versions, and to clarify both the glucose values (in mmol/L) and the dysglycemia categories.	Section 8.1
Updated the definition of CFRD to either fasting hyperglycemia (blood glucose level ≥ 126 mg/dL [≥ 7.00 mmol/L] after an 8-hour fast) or 2-hour post-OGTT blood glucose level ≥ 200 mg/dL (≥ 11.10 mmol/L) to eliminate a gap in glucose values in previous protocol versions, and to clarify both the glucose values (in mmol/L) and the dysglycemia categories.	Section 8.1
Updated text to state that height will be measured for all subjects at screening to correct an error in previous protocol versions.	Table 3-1 and Section 11.3.3
Added collection windows around the OGTT assessments and clarified that post-0 minute collection time points are defined as time after the start of ingestion of glucose solution to provide additional guidance on the execution of the OGTT assessment.	Table 3-1 and Table 3-2 , and Section 11.3.1

Change and Rationale	Affected Sections
Removed specification that only subjects with CFRD will collect an insulin diary, such that any subject who uses insulin will collect an insulin diary, to allow for the possibility of both IGT and CFRD subjects to be on insulin.	Synopsis, Table 3-2 , and Sections 7.3 , 11.3.4 , and 12.3.3.5
Added a waiver of the Safety Follow-up Visit for subjects who complete the Week 48 Visit and transition to a commercially available CFTR modulator regimen with 28 days after the last dose of study drug, given the possibility of commercial availability of ELX/TEZ/IVA in certain countries.	Section 9.1.3
Updated text that remote measures may be used for study visits at Week 4 and Week 12, but all other visits must be performed in the clinic, to provide clarity on the use of remote measures.	Section 9.1.7
Removed glyburide, nateglinide, and repaglinide from list of OATP1B1 and OATP1B3 substrates that should be used with caution to provide clarity and consistency within the protocol.	Section 9.5
Removed glimepiride and glipizide from list of CYP2C9 substrates that should be used with caution to provide clarity and consistency within the protocol.	Section 9.5
Added instruction for investigators to counsel subjects on safe withholding of insulins prior to each OGTT based on feedback from study sites.	Section 11.3.1
Added instruction for sites to record insulin use in the 24 hours prior to each OGTT, as insulin use may confound OGTT results.	Section 11.3.1

Typographical and administrative changes were also made to improve the clarity of the document.

2 PROTOCOL SYNOPSIS

Title A Phase 3b Open-label Study to Assess the Effect of Elexacaftor/Tezacaftor/Ivacaftor on Glucose Tolerance in Cystic Fibrosis Subjects with Abnormal Glucose Metabolism

Brief Title A Study to Assess the Effect of ELX/TEZ/IVA on Glucose Tolerance in Subjects With Cystic Fibrosis (CF)

Clinical Phase and Clinical Study Type Phase 3b, investigation of glucose tolerance

Objective Primary Objective

To evaluate the effect of elexacaftor (ELX)/tezacaftor (TEZ)/ivacaftor (IVA) on glucose tolerance in CF subjects with impaired glucose tolerance (IGT) or CF-related diabetes (CFRD)

Secondary Objective

To evaluate the safety and tolerability of ELX/TEZ/IVA

Endpoints Primary Endpoint

Change from baseline in 2-hour blood glucose levels following an oral glucose tolerance test (OGTT) to the average of Week 36 and Week 48

Secondary Endpoints

- Proportion of subjects with improvement in dysglycemia categorization (CFRD, IGT, normal glucose tolerance [NGT]) at Week 48
- Safety and tolerability of ELX/TEZ/IVA based on adverse events (AEs), clinical laboratory values, ECGs, vital signs, and pulse oximetry

Other Endpoints

- Change from baseline in sweat chloride (SwCl) through Week 48
- Absolute change in body mass index (BMI) from baseline at Week 48
- Absolute change in body weight from baseline at Week 48
- Change from baseline in hemoglobin A1c (HbA1c) and fructosamine at Week 48
- Change from baseline in insulin use (dose) at Week 48 in subjects using insulin
- Change from baseline in post-OGTT diabetes-related biomarkers (including insulin, C-peptide, glucagon, calculated indices of insulin secretion [insulinogenic index], and insulin resistance [HOMA-IR]) at Week 48
- Change from baseline in biomarkers of inflammation (including C-reactive protein [CRP]) at Week 48
- Change from baseline in biomarkers of pancreatic function (including fecal elastase-1 [FE-1] and serum immunoreactive trypsinogen [IRT]) at Week 48
- Change from baseline in post-OGTT incretin levels (including glucagon-like peptide 1 [GLP-1] and glucose-dependent insulinotropic polypeptide [GIP]) at Week 48
- Change from baseline in percent of time spent in target blood glucose range of ≥ 70 to < 140 mg/dL (≥ 3.89 to < 7.77 mmol/L) as measured by 7-day continuous glucose monitoring (CGM) in subjects with CFRD at Week 48

- Change from baseline in selected CGM parameters (including but not limited to percent of time spent between ≥ 140 and < 200 mg/dL [≥ 7.77 and < 11.10 mmol/L], percent of time spent ≥ 200 mg/dL [≥ 11.10 mmol/L], and maximum amplitude of glucose excursions [MAGE]) in subjects with CFRD at Week 48.

Number of Subjects Approximately 60 subjects will be enrolled, of whom approximately 30 subjects will have IGT and 30 subjects will have CFRD.

Study Population Male and female subjects with CF who are 12 years of age or older, heterozygous for the *F508del* mutation and an MF mutation (F/MF genotypes), with abnormal glucose tolerance as determined by OGTT at screening (classified as either IGT or CFRD). Among all subjects, approximately 50% may be enrolled while using insulin (≤ 0.3 units/kg/day).

Investigational Drug **Active substance:** ELX (VX-445)/TEZ (VX-661)/IVA (VX-770)
Activity: CFTR correctors (ELX and TEZ) and potentiator (IVA)
Strength and route of administration: ELX 100-mg/TEZ 50-mg/IVA 75-mg fixed-dose combination (FDC) tablets, oral

[figure not shown]
Active substance: IVA (VX-770)

Activity: CFTR potentiator

Strength and route of administration: 150-mg tablets, oral

Study Duration Excluding the Screening Period, the total study duration is approximately 52 weeks (48 weeks for the Treatment Period, and 4 weeks for the Safety Follow-up Period).

Study Design This is a Phase 3b, open-label study in CF subjects 12 years of age and older with F/MF genotypes and abnormal glucose tolerance. A schematic of the study design is shown in [Figure 2-1](#).

Figure 2-1 VX19-445-117 Study Design

ELX: elexacaftor; CFRD: CF-related diabetes; CGM: continuous glucose monitoring; IVA: ivacaftor; N: total sample size; TEZ: tezacaftor

- ^a On Day -7, a CGM sensor will be inserted subcutaneously to assess baseline blood glucose levels for 7 days prior to the first dose of study drug in subjects with CFRD.
- ^b Subjects who complete the visits in the Treatment Period, regardless of whether they are on a treatment interruption, will be offered the opportunity to enroll in an open-label extension safety study evaluating ELX/TEZ/IVA. The Safety Follow-up Visit is not required for subjects who complete the Week 48 Visit and have enrolled in an open-label study within 28 days after the last dose of study drug.

Subjects will receive ELX 200 mg once daily (qd)/TEZ 100 mg qd/IVA 150 mg every 12 hours (q12h).

Assessments Efficacy and PD:

- 2-hour OGTT
- SwCl
- BMI
- Weight
- Height
- Diabetes-related blood biomarkers collection
- Insulin use diary for subjects using insulin
- CGM (subjects with CFRD only)

Safety: AEs, clinical laboratory assessments, 12-lead ECGs, vital signs, pulse oximetry, ophthalmologic examinations (for subjects <18 years of age on the date of informed consent), and physical examinations (PEs)

Other:

- Spirometry
- Fecal sample collection
- Other blood biomarkers collection

Statistical Analyses Statistical analysis details will be provided in the Statistical Analysis Plan (SAP), which will be finalized before the clinical database lock.

The primary null hypothesis to be tested is that the mean change from baseline in 2-hour blood glucose levels following OGTT to the average of Week 36 and Week 48 is equal to zero. Assuming a within group SD of 45 mg/dL and a 10% dropout rate at Week 48, a sample size of 60 subjects will have more than 95% power to detect a mean decrease from baseline of -30 mg/dL in 2-hour blood glucose levels

post-OGTT to the average of Week 36 and Week 48, based on a 2-sided, 1-sample *t*-test at a significance level of 0.05 using the EAST software Version 6.4.

The primary analysis will be based on a mixed-effects model for repeated measures (MMRM) with change from baseline in 2-hour post-OGTT blood glucose levels at Weeks 24, 36, and 48 as the dependent variable. The model will include visit as a fixed effect, and will be adjusted for main covariates as appropriate. The primary result obtained from the model will be the estimated mean change from baseline to the average of Week 36 and Week 48. The estimated change at each visit and the mean change to the average of Week 36 and Week 48 along with the 2-sided 95% CI and *P* value will be provided.

3 SCHEDULE OF ASSESSMENTS

Schedules of assessments are in [Table 3-1](#) and [Table 3-2](#).

Table 3-1 Study VX19-445-117: Screening

Event/Assessment	Screening Visit Day -35 to Day -8	Comments
Study visit	X	The Screening Visit must be performed in the clinic.
Informed consent (and assent, if applicable)	X	Electronic or remote consent may be used, if permitted by local regulations.
Demographics	X	Section 11.1
Medical history	X	Section 11.1
Medications review	X	Information regarding medications taken within 56 days before the Screening Visit will be collected (Section 9.5).
Height and weight	X	Measured with shoes off (Section 11.3.3).
Vital signs and pulse oximetry	X	Collected after the subject has been at rest for at least 5 minutes (Section 11.4.3).
Ophthalmologic examination	X	Conducted by an ophthalmologist or optometrist for subjects <18 years of age on the date of informed consent (Section 11.4.5).
Complete physical examination	X	Section 11.4.3
12-lead ECG	X	Performed prior to any procedure that may affect heart rate (e.g., blood draws) and after subject has been at rest for at least 5 minutes (Section 11.4.4).
Sweat chloride	X	Section 11.3.5
Spirometry	X	Performed pre- or post-bronchodilator (Section 11.2.1)
CF genotype	X	If the CFTR genotype result is not received before the first dose of study drug, a previous CFTR genotype laboratory report may be used to establish eligibility (Section 8.1). Subjects who have been enrolled whose screening genotype does not confirm study eligibility must be discontinued from the study (Section 9.9).
Serum pregnancy (all female subjects)	X	Section 11.4.2
Serum chemistry (including cholesterol and thyroid-stimulating hormone)	X	
Hematology	X	
Coagulation	X	
Urinalysis	X	
Oral glucose tolerance test (OGTT)	X	If permitted by local regulations, subjects may provide informed consent remotely to begin fasting (except water and allowed medications other than prednisone and prednisolone) at least 8 hours before the OGTT at the Screening Visit. Blood glucose levels will be measured at 0, 30 (± 5), 60 (± 5), 90 (± 5), and 120 (± 5) minutes after the start of consuming 1.75 g/kg of body weight (maximum of 75 g total) of glucose solution (Section 11.3.1).
OGTT blood biomarkers collection	X	Collected on the same day as the OGTT (Section 11.3.1).
Fecal sample collection	X	Fecal sample may be collected at the site during the Screening Visit, or at any time point prior to the first dose of study drug (Section 11.2.2).

Table 3-1 Study VX19-445-117: Screening

Event/Assessment	Screening Visit Day -35 to Day -8	Comments
Adverse events	Continuous, From the Date of Informed Consent through Completion of Study Participation	Section 13.1; completion of study participation is defined in Section 9.1.6.

CF: cystic fibrosis; OGTT: oral glucose tolerance test

Table 3-2 Study VX19-445-117: Treatment Period and Safety Follow-up Visit

Event/ Assessment ^a	Day -7 (± 1 day) ^b	Treatment Period							ETT Visit	Safety Follow-up Visit (28 ± 7 Days After Last Dose of Study Drug) ^c	Comments
		Day 1	Week 4 (± 5 days)	Weeks 8, 16, 20, 28, 32, 40, 44 (± 5 days)	Week 12 (± 5 days)	Week 24 (± 5 days)	Week 36 (± 5 days)	Week 48 (± 5 days)			
Study visit	X	X	X		X	X	X	X	X	X	The Week 4 and Week 12 visits may be performed either in the clinic or as a home health visit, if permitted by local regulations. See Section 9.1.7 for use of remote measures in extenuating circumstances. All home health visits must have a consultation between the subject and investigator (i.e., in person, phone, or telemedicine video conference) within 1 business day after the home health visit; this consultation can be outside the visit window.
Telephone contact or telemedicine video conference				X							Assess subject's status, any AEs, concomitant medications, treatments, and procedures.

^a All assessments will be performed before dosing unless noted otherwise.

^b The Day -7 Visit only applies to subjects with CFRD.

^c The Safety Follow-up Visit is not required for subjects who complete the Week 48 Visit and have enrolled in an open-label study within 28 days.

Table 3-2 Study VX19-445-117: Treatment Period and Safety Follow-up Visit

Event/ Assessment ^a	Day -7 (± 1 day) ^b	Treatment Period							ETT Visit	Safety Follow-up Visit (28 ± 7 Days After Last Dose of Study Drug) ^c	Comments
		Day 1	Week 4 (± 5 days)	Weeks 8, 16, 20, 28, 32, 40, 44 (± 5 days)	Week 12 (± 5 days)	Week 24 (± 5 days)	Week 36 (± 5 days)	Week 48 (± 5 days)			
Safety and Efficacy Assessments											
Ophthalmologic examination								X at or up to 4 weeks before	X		Conducted by an ophthalmologist or optometrist for subjects <18 years of age on the date of informed consent (Section 11.4.5). Subjects who complete at least 12 weeks of study drug treatment will have a single ophthalmologic examination at either the ETT or Week 48 Visit, whichever comes first.
Complete physical examination		X						X	X		Symptom-directed physical examinations will occur at any time during the study if deemed necessary by the investigator (Section 11.4.3).
Height and weight		X	X		X	X	X	X	X	X	Measured with shoes off. Height will only be collected for subjects <21 years of age on the date of informed consent (Section 11.3.3).
Vital signs and pulse oximetry		X	X		X	X	X	X	X	X	Collected after the subject has been at rest for at least 5 minutes (Section 11.4.3).

Table 3-2 Study VX19-445-117: Treatment Period and Safety Follow-up Visit

Event/ Assessment ^a	Day -7 (± 1 day) ^b	Treatment Period							ETT Visit	Safety Follow-up Visit (28 ± 7 Days After Last Dose of Study Drug) ^c	Comments
		Day 1	Week 4 (± 5 days)	Weeks 8, 16, 20, 28, 32, 40, 44 (± 5 days)	Week 12 (± 5 days)	Week 24 (± 5 days)	Week 36 (± 5 days)	Week 48 (± 5 days)			
12-lead ECG		X				X		X	X	X	Performed prior to any procedure that may affect heart rate (e.g., blood draws) and after subject has been at rest for at least 5 minutes (Section 11.4.4).
Oral glucose tolerance test (OGTT)		X				X	X	X			After at least an 8-hour fast (except water and allowed medications other than prednisone and prednisolone). Blood glucose levels will be measured at 0, 30 (±5), 60 (±5), 90 (±5), and 120 (±5) minutes after the start of consuming 1.75 g/kg of body weight (maximum of 75 g total) of glucose solution (Section 11.3.1).
OGTT blood biomarkers collection		X				X	X	X			Collected on the same days as the OGTT (Section 11.3.1)
CGM sensor inserted (subjects with CFRD only)	X	X			X	X	X	X			The CGM sensor will be inserted and worn for approximately 7 days (Section 11.3.2).
Sweat chloride		X				X		X	X		Section 11.3.5
Blood collection for HbA1c and fructosamine		X	X		X	X	X	X	X		

Table 3-2 Study VX19-445-117: Treatment Period and Safety Follow-up Visit

Event/ Assessment ^a	Day -7 (± 1 day) ^b	Treatment Period							ETT Visit	Safety Follow-up Visit (28 ± 7 Days After Last Dose of Study Drug) ^c	Comments
		Day 1	Week 4 (± 5 days)	Weeks 8, 16, 20, 28, 32, 40, 44 (± 5 days)	Week 12 (± 5 days)	Week 24 (± 5 days)	Week 36 (± 5 days)	Week 48 (± 5 days)			
Pregnancy test (all female subjects)		Urine	Urine	Urine	Urine	Urine	Urine	Urine	Serum	Serum	At telephone contacts, a urine pregnancy test will be performed with a home kit provided by the study site. Results will be reported to the site by telephone (Section 11.4.2).
Serum chemistry		X	X		X	X	X	X	X	X	Section 11.4.2
Hematology		X	X		X	X	X	X	X	X	
Coagulation		X				X		X	X	X	
Urinalysis		X						X	X	X	
Insulin diary for insulin users		X	X		X	X	X	X	X		At each study visit the subject will provide the diary for documentation of insulin use (Section 11.3.4)
Adverse events	Continuous, From the Date of Informed Consent through Completion of Study Participation										Completion of study participation is defined in Section 9.1.6.
Medications review	Continuous, From the Date of Informed Consent through Completion of Study Participation										
Treatment and procedures review	Continuous, From the Date of Informed Consent through Completion of Study Participation										
Other Assessments											
Blood biomarker collection for pancreatic markers		X	X		X	X		X	X		Section 11.2.3

Table 3-2 Study VX19-445-117: Treatment Period and Safety Follow-up Visit

Event/ Assessment ^a	Day -7 (± 1 day) ^b	Treatment Period							ETT Visit	Safety Follow-up Visit (28 ± 7 Days After Last Dose of Study Drug) ^c	Comments
		Day 1	Week 4 (± 5 days)	Weeks 8, 16, 20, 28, 32, 40, 44 (± 5 days)	Week 12 (± 5 days)	Week 24 (± 5 days)	Week 36 (± 5 days)	Week 48 (± 5 days)			
Blood biomarker collection for inflammatory markers		X	X		X	X		X	X		Section 11.2.3
Fecal sample collection		X				X		X			Samples may be collected by the subject or the subject's caregiver up to 48 hours before the study visit at home and brought to the study visit (Section 11.2.2). The Day 1 sample must be collected predose; others may be collected pre- or postdose. Subjects who provide a fecal sample at the Screening Visit, or at any time point prior to the first dose of study drug, do not need to provide a sample on Day 1.

Table 3-2 Study VX19-445-117: Treatment Period and Safety Follow-up Visit

Event/ Assessment ^a	Day -7 (± 1 day) ^b	Treatment Period							ETT Visit	Safety Follow-up Visit (28 ± 7 Days After Last Dose of Study Drug) ^c	Comments
		Day 1	Week 4 (± 5 days)	Weeks 8, 16, 20, 28, 32, 40, 44 (± 5 days)	Week 12 (± 5 days)	Week 24 (± 5 days)	Week 36 (± 5 days)	Week 48 (± 5 days)			
Spirometry		X	X			X		X	X		Performed pre-bronchodilator, before the AM dose, and at approximately the same time at each visit (Section 11.2.1). During in-clinic visits, spirometry assessments may be performed on more than one spirometer, as applicable.
Study Drug Administration											
Study drug dosing		ELX/TEZ/IVA Day 1 through evening before Week 48 Visit									Administered within approximately 30 minutes of consuming fat-containing food (e.g., standard “CF” meal or snack) (Section 9.6.1). On scheduled visits, the morning dose of study drug will be administered under the supervision of site medical staff or a home health nurse after predose assessments have been completed (food to be provided by site on in-clinic visit days).
Study drug count			X		X	X	X	X	X		

Table 3-2 Study VX19-445-117: Treatment Period and Safety Follow-up Visit

Event/ Assessment ^a	Day -7 (± 1 day) ^b	Treatment Period							ETT Visit	Safety Follow-up Visit (28 ± 7 Days After Last Dose of Study Drug) ^c	Comments
		Day 1	Week 4 (± 5 days)	Weeks 8, 16, 20, 28, 32, 40, 44 (± 5 days)	Week 12 (± 5 days)	Week 24 (± 5 days)	Week 36 (± 5 days)	Week 48 (± 5 days)			

AE: adverse event; CF: cystic fibrosis; CFRD: cystic fibrosis related diabetes; CGM: continuous glucose monitoring; ELX: elxacaftor; ETT: early termination of treatment; HbA1c: hemoglobin A1c; IRT: immunoreactive trypsinogen; IVA: ivacaftor; OGTT: oral glucose tolerance test; TEZ: tezacaftor

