7.3 Other Endpoints

- Change from baseline in sweat chloride (SwCl) through Week 48
- Absolute change in body mass index (BMI) from baseline at Week 48
- Absolute change in body weight from baseline at Week 48
- Change from baseline in hemoglobin A1c (HbA1c) and fructosamine at Week 48
- Change from baseline in insulin use (dose) at Week 48 in subjects using insulin
- Change from baseline in post-OGTT diabetes-related biomarkers (including insulin, C-peptide, glucagon, calculated indices of insulin secretion [insulinogenic index], and insulin resistance [HOMA-IR]) at Week 48
- Change from baseline in biomarkers of inflammation (including C-reactive protein [CRP]) at Week 48
- Change from baseline in biomarkers of pancreatic function (including fecal elastase-1 [FE-1] and serum immunoreactive trypsinogen [IRT]) at Week 48
- Change from baseline in post-OGTT incretin levels (including glucagon-like peptide 1 [GLP-1] and glucose-dependent insulinotropic polypeptide [GIP]) at Week 48
- Change from baseline in percent of time spent in target blood glucose range of ≥ 70 to < 140 mg/dL (≥ 3.89 to < 7.77 mmol/L) as measured by 7-day continuous glucose monitoring (CGM) in subjects with CFRD at Week 48
- Change from baseline in selected CGM parameters (including but not limited to percent of time spent between ≥ 140 and < 200 mg/dL [≥ 7.77 and < 11.10 mmol/L], percent of time

spent ≥ 200 mg/dL [≥ 11.10 mmol/L], and maximum amplitude of glucose excursions [MAGE]) in subjects with CFRD at Week 48

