9.1.3 Follow-up

The Safety Follow-up Visit is scheduled to occur 28 (\pm 7) days after the last dose of study drug. The Safety Follow-up Visit is not required for subjects who complete the Week 48 Visit and enroll in the open-label extension safety study, or who transition to a commercially available CFTR modulator regimen, within 28 days after the last dose of study drug.

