9.1.6 Completion of Study Participation

Completion of study participation for each individual subject is defined as 1 of the following:

- For subjects who complete the Treatment Period and enter an open-label extension safety study within 28 days of the Week 48 Visit: the Week 48 Visit
- For subjects who complete the Treatment Period and do not enter an open-label extension safety study within 28 days of the Week 48 Visit: the Safety Follow-up Visit
- For subjects who prematurely discontinue study drug treatment but do not withdraw consent (and assent, as applicable): the latest of the ETT Visit or Safety Follow-up Visit (if required)
- For subjects who withdraw consent or assent: date of withdrawal of consent or assent, whichever is earlier (Section 9.9)

If subjects are lost to follow-up (Section 9.1.5), the date of completion of study participation will be defined as the date of the last contact.

The end of study is defined in Section 13.2.9.

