9.3.2 Study Population

This study will enroll CF subjects with F/MF genotypes, 12 years of age and older. A pivotal Phase 3 study demonstrated efficacy and safety of ELX/TEZ/IVA in CF subjects with F/MF genotypes 12 years of age and older. The F/MF population has the highest incidence of abnormal glucose tolerance, as defined by an OGTT, including IGT and CFRD. This is due to stereotypical progression of pancreatic disease, including blocked acinar ducts, atrophy of the exocrine pancreas, loss of endocrine islets, inflammation, additional genetic factors, and other potential mechanisms as described above. Patients with F/MF genotypes therefore offer a population of patients who are naive to CFTR modulator treatment and have prevalent endocrine disease (IGT/CFRD) that is amenable to investigation.

This study will utilize both the OGTT and CGM to evaluate the effect of ELX/TEZ/IVA on abnormal glucose homeostasis in subjects with CF and F/MF genotypes.

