9.6 Administration

9.6.1 Dosing

Study drug tablets will be administered orally as ELX 200 mg qd/TEZ 100 mg qd/IVA 150 mg q12h.

Study drug should be administered with a fat-containing meal or snack, such as a standard “CF” meal or snack or a standard meal according to the following guidelines:

1. It is recommended that the dose be taken within approximately 30 minutes of the start of the meal or snack.
2. All doses of study drug (morning and evening, as applicable) should be administered at approximately every 12 hours (\pm 2 hours) on each dosing occasion (e.g., if the morning doses of study drug are administered at 08:00 hour on Day 1, all subsequent morning doses should be administered between 06:00 hour and 10:00 hour).
3. At the Day 1 Visit, all subjects will be observed for 2 hours after the morning dose of the study drug.
4. On days of scheduled visits, the morning dose of study drug will be administered under the supervision of site medical staff or a home health nurse after predose assessments have been completed. The meal or snack will be provided by the site on in-clinic visit days for the morning dose of study drug.
5. For visits after the Day 1 Visit, subjects will be instructed to return all used and unused study drug to the site or the home health nurse; study drug will be dispensed at each visit, as appropriate.
6. At the Week 48 Visit, the morning dose of study drug will NOT be administered. The last dose of study drug will be the evening dose administered the day before the Week 48 Visit.

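### The last CGM sensor goes in after study dosing has ended, so the CGM change at Week 48 contains no scheduled dosing day and should be moved or labelled

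*Protocol*

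**What the plan says.** **CGM timing.** Protocol Table 3-2 marks sensor insertion, for subjects with CFRD only, at Day -7, Day 1 and Weeks 12, 24, 36 and 48. There is no mark at the early-termination or Safety Follow-up visits. The comment reads "The CGM sensor will be inserted and worn for approximately 7 days (Section 11.3.2". Section 11.3.2 refers back to the same table for timing.

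**Dosing.** The dosing row of Table 3-2 reads "ELX/TEZ/IVA Day 1 through evening before Week 48 Visit". Section 9.6.1, item 6, withholds the morning dose at that visit and adds: "The last dose of study drug will be the evening dose administered the day before the Week 48 Visit".

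**Endpoint and purpose.** Section 7.3 defines the change in percent of time in the target glucose range "as measured by 7-day continuous glucose monitoring (CGM) in subjects with CFRD at Week 48", and further CGM parameters at the same time point. Section 9.3.2 gives the purpose: "This study will utilize both the OGTT and CGM to evaluate the effect of ELX/TEZ/IVA on abnormal glucose homeostasis".

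**Analysis.** SAP Table 11-1 gives Week 48 CGM a target of Day 337 and a window of (295, 362]. SAP 8.3.3.1 averages all valid days if at least 4 are valid, with no condition on drug status. SAP 8.3.3.2 summarises the percent-of-time measures descriptively at Week 48 and at each earlier post-baseline visit. SAP 8.5 leaves MAGE and some other CGM parameters to a separate document.

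**The concern.** A sensor records forward from insertion. The protocol allows for this at baseline, where a separate Day -7 visit lets the recording finish before the first dose. The end of treatment has no counterpart: the sensor goes in at the visit that follows the last dose.

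The result reported as the change at Week 48 therefore sets one week before dosing against one week after scheduled dosing. A reader would take it as the effect on daily glucose after 48 weeks of treatment, which is the use that Section 9.3.2 gives CGM. If glucose control shifts once dosing stops, the figure would miss part of the on-treatment effect. If some subjects have already started extension or commercial drug, it would average over different drug states. Neither possibility would be visible in the planned tables.

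**Working it through.** **Reproducing the SAP days.** Target day = 7 × week + 1. Week 36: 7 × 36 + 1 = 253. Week 48: 7 × 48 + 1 = 337. The lower limit of the Week 48 window is the midpoint, (253 + 337)/2 = 295. All three match SAP Table 11-1. The upper limit is 362 - 337 = 25 days after target for CGM, against 351 - 337 = 14 days for OGTT. The wider limit, and the label Week 1 for the Day 1 insertion, fit a recording that runs forward from the visit.

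**Counting scheduled dosing days in each wear.** Let V be the day of the Week 48 Visit. With the ±5-day window in Table 3-2, V runs from 332 to 342. Scheduled dosing covers Day 1 to Day V - 1, so the last dosing day is 331 at the earliest. A 7-day wear covers the insertion day and the next 6 days.

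| Insertion | Insertion days | Earliest wear | Latest wear | Dosing days in wear |
|---|---|---|---|---|
| Day 1 | 1 | 1-7 | 1-7 | 7 of 7 |
| Week 12 | 80-90 | 80-86 | 90-96 | 7 of 7 |
| Week 24 | 164-174 | 164-170 | 174-180 | 7 of 7 |
| Week 36 | 248-258 | 248-254 | 258-264 | 7 of 7 |
| Week 48 | 332-342 | 332-338 | 342-348 | 0 of 7 |

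At Week 48 the wear starts on Day V and the last dose falls on Day V - 1, so the count is 0 for every allowed visit day. Counting to the same clock time a week later adds one calendar day to each wear and leaves 0 unchanged. All Week 48 wear days lie inside (295, 362].

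**Could Week 36 data enter the Week 48 window?** The latest Week 36 wear ends on Day 264, or Day 265 with the extra calendar day. The window opens on Day 296. The gap is 296 - 264 = 32 or 296 - 265 = 31 days, so no. An unscheduled early insertion could add dosing days, but none is planned.

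**Subjects affected.** The plan enrols about 30 subjects with CFRD. If the 10% dropout assumed for the whole trial applies to them, 30 × 0.9 = 27 would reach Week 48.

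**Checking the proposed timing.** Insert on Day I = V - 7, which is Day 330 for a visit planned on Day 337. Wear is Days 330-336 and the last dose is on Day 336, so 7 of 7 days carry a scheduled dose. Over the visit window I runs from 325 to 335, always above 295. A valid day needs 202 readings × 5 min = 1,010 min, or about 16.8 hours, so the insertion day may not qualify. Full days up to the last dose number V - I - 1 = 6, against the 4 required. One day's late insertion leaves 5. A visit brought forward by k days leaves 6 - k, so the rule can still be met for k up to 2. A visit that slips later loses nothing, because dosing continues to the evening before it.

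**The case against.** The strongest reply is that little depends on this. The endpoints are in the protocol's other category, descriptive and untested, and confined to subjects with CFRD. CGM during dosing is scheduled at four earlier time points, and SAP 8.3.3.2 already summarises each of them. The extension study gives the same ELX/TEZ/IVA. Table 9-1 also bars other CFTR modulators for 28 days before Day 1 as possible confounders, so the plan itself allows that a modulator's influence could outlast a week. The Week 48 recording may therefore still reflect treatment.

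Most of that stands, and it sets the severity. It does not remove the point that the one CGM time point named in the endpoint is the one with no scheduled dosing, and that the tables do not say so.

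Four stronger readings are tempting but not supported:

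- *Subjects are off drug during the Week 48 wear.* The count concerns scheduled study doses, not exposure. The documents give no half-lives and no extension start dates.
- *The recording mixes drug states.* It may. Subjects can enter the extension, or be among those "who transition to a commercially available CFTR modulator regimen, within 28 days after the last dose of study drug", but nothing shows how many would do so within the week of wear.
- *Section 9.5 keeps subjects off new modulators during the wear.* Its general limit on new long-term medication should not be read that way. Table 9-1 deals with CFTR modulators specifically and ends their restriction after the last study dose.
- *Rollover status gives drug status during wear.* It does not. Entry may occur at any time within 28 days, while the wear lasts about 7.

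**Conclusion.** The concern holds as a timing and labelling fault of minor severity. As scheduled, the Week 48 CGM wear has 0 of 7 study-dosing days, and no scheduled recording made during dosing can fall in its analysis window. The change at Week 48 therefore compares the week before the first dose with the week after the last scheduled dose.

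This rests on insertion at the visit, forward wear of about 7 days, and dosing that stops as written. It affects at most about 30 subjects, or about 27 under the dropout assumption. The size and direction of any bias cannot be computed from the documents. The primary and secondary OGTT endpoints are unaffected, because the Week 48 OGTT is done at the visit itself. The trial is not without CGM during treatment; the last such recording is at Week 36.

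**What to change.** **If Week 48 visits are still to come.** Leave dosing unchanged and move the existing last insertion to about 7 days before the planned Week 48 Visit. Dispense the sensor at Week 36 for insertion by the trained subject, which Section 11.3.2 already permits. In SAP Table 11-1 set the Week 48 CGM target to about Day 330, keep the lower limit of 295, and count only CGM days up to the last study dose.

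The cost is a protocol amendment and an insertion away from a clinic visit. Subjects who cannot insert the sensor themselves would need a home nurse. The amendment must then make an allowance, because Section 9.1.7 ordinarily keeps visits other than Weeks 4 and 12 in the clinic. The number of sensors stays at 6 per subject. A visit brought forward by more than 2 days could leave too few valid days, so the insertion date should follow the booked visit.

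**If visits have already taken place.** Label the Week 48 CGM *recorded after the last scheduled study dose*, both in the SAP and in the separate document named in SAP 8.5. Present the already planned Week 36 summary beside it as the last scheduled CGM during dosing. Split the Week 48 result by drug status during wear only where start dates are available. For extension entrants the study's own records may not hold them: Section 9.1.6 defines completion, for those who "enter an open-label extension safety study within 28 days of the Week 48 Visit: the Week 48 Visit", and Table 3-2 runs medication review only to completion. This route costs a label and, where the data allow, one extra descriptive split.
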